Study to Evaluate the Safety and Efficacy of Oral Insulin Formulation in Type 2 Diabetes Mellitus Subjects

NCT06473662

06/19/2024

STUDY OBJECTIVES

Primary Objective

To evaluate the safe and effective dose of USVCAP (75 IU, or 150 IU, or 300 IU) after twice daily treatment with selected fixed dose (75 IU, or 150 IU, or 300 IU) of USVCAP for 12 weeks

Secondary Objective

To assess the immunogenicity of the investigational product

INVESTIGATIONAL PLAN

Overall Study Design and Plan-Description

Overview of Study Design

This was a phase IIb, open-label, randomized, comparative study to evaluate the safety and efficacy of USVCAP formulation in T2DM subjects uncontrolled with metformin hydrochloride treatment.

Total of 153 subjects who met the eligibility criteria were randomized in a ratio of 1:1:1 to any one of the following 3 treatment groups:

- Group A: USVCAP 75 IU, BD for 12 weeks
- Group B: USVCAP 150 IU, BD for 12 weeks
- Group C: USVCAP 300 IU, BD for 12 weeks

Each subject had following study periods and visits:

- Screening period (Visit 1): It lasted for up to 21 days after signing the informed consent form (ICF)
- Treatment period (Visit 2 to Visit 7): Eligible subjects were randomly assigned to any one of the above treatment groups at Visit 2 by randomization process through an interactive web response system (IWRS). Each subject from all 3 treatment groups received *assigned fixed dose of USVCAP (i.e. IP) as per allocated treatment groups for 12 weeks.

*Assigned fixed dose in the study is defined as: Fixed dose of USVCAP (i.e. IP) administered to subject twice daily for 12 weeks based on the treatment group (Group A, Group B, or Group C) allocated at randomization visit.

- Upon randomization:
 - Subjects allocated to Group A were prescribed with the assigned fixed dose of USVCAP (75 IU BD) from next day of randomization (Day 1) for 12 weeks
 - Subjects allocated to Group B and Group C, underwent a run-in period of 1 week with each previous lower dose/s, prior to initiation of assigned fixed dose of USVCAP. They additionally visited the study site for a step-wise increase of dose/s at each run-in period/s. These visits were called dose escalation (DE) visits (Visit DE 1 and Visit DE 2) in the trial. The dose increase were done once for Group B and twice for Group C subjects as depicted in Table 2 and Table 3. Upon completion of the run-in period/s, the

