One hundred and fifty-three (153) subjects were enrolled in the study. These subjects were randomized in a ratio of 1:1:1 to receive IP from any one of the following 3 treatment groups:

- Group A: USVCAP 75 IU, BD for 12 weeks
- Group B: USVCAP 150 IU, BD for 12 weeks
- Group C: USVCAP 300 IU, BD for 12 weeks

Eligible subjects were randomly assigned to any one of the above treatment groups by a randomization code generated by an interactive web response system (IWRS).

The subjects were randomized in the study using permuted block randomization into 3 treatment groups. The randomization list was prepared using a validated computer program, statistical analysis system[®] (SAS[®]) for Windows version 9.4/Proc PLAN (SAS[®] Institute Inc., Cary, NC, USA). An IWRS method containing randomization codes was used to randomize the eligible subject to the treatment groups.

Selection of Doses in the Study

The investigational product, USVCAP was administered at doses 75 IU, 150 IU, and 300 IU, orally, twice daily.

Selection and Timing of Dose for Each Patient

Each subject allocated to treatment Groups A, B, or C received treatment with USVCAP IP as follows:

For subjects randomized to Group A (USVCAP 75 IU BD for 12 weeks) administered the IP as follows:

USVCAP 75 IU BD: Day 1 until Day 84

For subjects randomized to Group B (i.e. USVCAP 150 IU BD for 12 weeks) and Group C (i.e. USVCAP 300 IU BD for 12 weeks):

Therewas a run-in period/s of 1 week with each lower dose/s prior to initiation of the assigned fixed dose of USVCAP (Table 2). Upon completion of the run-in period/s, the subjects received the assigned fixed dose of USVCAP further for 12 weeks.

Blinding

Not applicable as this is an open-label study.

Maintenance of Study Treatment Randomization Codes

Final randomization list and codes are kept strictly confidential and are filed securely by the independent biostatistician. The randomization codes were accessible only to authorized persons until completion of the study.

Emergency Unblinding of an Individual Subject in the Study

Not applicable as this is an open-label study.

Medication(s)/Treatment(s) Permitted and Not Permitted Before and/or During the Study

Prior medication

All subjects were enquired for prior treatment/surgery at the time of screening:

- Surgical and medical history (including T2DM history) were recorded

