The efficacy assessments HbA1c, FPG and 2-hour PPG were assessed at the central laboratory identified for the study.

It was performed as follows:

- At screening to confirm the eligibility of the subject in the study
- During the treatment period and at EOT to evaluate to assess the safety and the treatment response
- At the EOS to evaluate the post-treatment safety of the subjects after twice daily administration of IP for 12 weeks

The blood samples for HbA1c, FPG and 2-hour PPG were withdrawn from the subject for the following tests:

- Glycated haemoglobin at Visit 1 and Visit 7
- Fasting plasma glucose level under fasting condition i.e. at least 8–10 hours of overnight fasting at Visits 1, 3, 4, 6, and 7 for all subjects

For Group B subjects: Prior to Visit DE 1

For Group C subjects: Prior to Visit DE 1 and Visit DE 2

• Postprandial glucose level (2-hours after meal) at Visits 1, 3, 4, 6 and 7 for all subjects. For Group B subjects: Prior to Visit DE 1

For Group C subjects: Prior to Visit DE 1 and Visit DE 2

• All samples were sent to central laboratory for evaluation. FPG and 2-hour PPG test results at Visit DE 1 and Visit DE 2 should be available prior to dosing.

Capillary glucose measurements

Capillary glucose measurements were performed by the subjects using a self-monitoring blood glucose device throughout the treatment period (from Visit 2 to Visit 7), once every week (mid-week).

During run-in period(s) (from Visit 2 to DE 1 [in Group B subjects] and from Visit 2 to Visit DE 1 and from Visit DE 1 to Visit DE 2 [in Group C] subjects), capillary glucose measurements were performed at mid-week.

The capillary glucose measurements were performed at the following 4 time points:

- Fasting: After 8 hours of overnight fast
- 2-hours post-breakfast
- 2-hours post-lunch
- 2-hours post-dinner

The measurements for all 4 timepoints were performed on the same day. All capillary glucose measurements were recorded by subject in the respective visit subject diary.

Hypoglycemia

It was important for subjects in the study to recognize signs and symptoms of hypoglycemia. Subjects enrolled in the study were educated on signs and symptoms of hypoglycemia and were instructed to keep glucose tablets handy & take 4 glucose tablets (total 15 -20 grams of glucose) immediately to treat hypoglycemia, if it occurs.

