In any case, all study records are for at least 5 years after the completion or discontinuation of the study. The Investigator notified sponsor or its designee of any changes in the archival arrangements, including but not limited to archival at an off-site facility, transfer of ownership of the records in the event the Investigator left the site. Sponsor notified the Investigator in writing when the study-related records were no longer needed.

Statistical Methods Planned in the Protocol and Determination of Sample Size

The following is an outline of the statistical methodology that was used to report and analyse this study. A more detailed description is provided in a separate statistical analysis plan (SAP) that includes additional exploratory analysis not explicitly mentioned in the following sections.

Study Analyses Sets

The analyses was performed on the following trial populations.

- Randomized population: The randomized population consisted of all subjects who were randomized in the study
- Safety population: The safety population consisted of all subjects who were randomized and had received at least one dose of the IP.
- Full Analysis Population: The full analysis set population consists of all the subjects who are randomized into the study, received at least one dose of the IP from the assigned dose by randomization, and had at least one post baseline assessment.
- Per Protocol (PP) population: The per-protocol (PP) population was all the subjects in the FAS population who had completed the study and did not had any major protocol deviation.

Demographic and Other Baseline Characteristics

The demographic variables such as age, gender, ethnicity, body weight and height etc. and baseline status (medical history, physical exam, etc.) was summarized for both PP and full analysis populations.

The descriptive statistics for continuous variables were presented with number (n) of nonmissing observations, missing observations, Mean, Standard Deviation (SD), Median, Minimum and Maximum. For categorical data, descriptive statistics were presented with number of exposed subjects, and number (N) with percentage of observations in the various categories of the endpoint, where percentage were based on the exposed subjects.

Descriptive statistics were provided for body weight, waist circumference and BMI parameters. In addition, individual results were reviewed for any treatment-emergent changes of possible clinical significance.

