
Study termination by Sponsor: Upon notification of the sponsor for termination of the study

Study termination based on the advice by CDSCO or any other competent authority: If the regulatory authority(ies) directly connects to the site/CRO to terminate the study, the same was immediately done by the Investigator/information were communicated to the sites. The CRO must notify the site regarding such communications. In case of communications directly reaching the Investigator, the Investigator must inform the CRO designee (e.g. study site monitor) or both Sponsor designee and CRO designee

Any, other reason: If none of the above-mentioned reasons are applicable, then the reason for subject withdrawal were mentioned; "any other reason" and the reason were specified on the eCRF page. In case of pregnancy, the subject's study treatment must permanently stop and study discontinuation and early withdrawal procedures should be conducted.

Determination of Sample Size

It was estimated that 52 evaluable subjects per dose group were needed to be enrolled in each treatment group assuming a reduction of 0.5 in HbA1c, common standard deviation (SD) of 1.0 at baseline and at Week 12 in each dose group with 90% power and 2.5% level of significance. However, 13 extra subjects, accounting for 65 subjects per group in total were enrolled into this study with an aim to compensate for an estimated drop-out rate of 20%. Thus, a total number of 195 subjects were to be randomly assigned to either of the three dose (treatment) groups in this study in the ratio of 1:1:1. The detailed description of sample size calculation is represented in the table below:

Single Mean - Paired t-test				
Pre-test mean	7.5			
Post-test mean	7			
Mean Difference from Pre-to Post test	0.5			
Standard deviation in Pre-test	1			
Standard deviation in Post-test	1			
Effect size	0.5			
Power (%)	90			
Alpha Error	2.5			
1 or 2 sided	2			
Minimum required sample size for each selected fixed dose treatment	52			

group	
Minimum required sample size for all three-selected fixed dose treatment	156
groups	
Considering 20% drop-out, required sample size for each selected fixed	65
dose treatment group per	
Considering 20% drop-out, required sample size for all three-selected	
fixed dose treatment groups	195

Missing Data

The missing observations were imputed using Last Observation Carried Forward (LOCF) appropriately.

Procedures for Reporting Deviations from Original Statistical Plan

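### The sample-size section says 65 per group (195 in all) were enrolled to secure 90% power, but 153 were randomised: fewer than the plan's own 156 evaluable, and the shortfall is not recorded

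*Combined protocol and SAP*

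**What the plan says.** In the combined protocol and SAP, Determination of Sample Size begins: "It was estimated that 52 evaluable subjects per dose group were needed". The basis is a paired t-test within each dose group, a fall of 0.5 in HbA1c, SD 1.0 before and after, 90% power and a two-sided 2.5% level. Thirteen subjects per group are added for 20% drop-out, "accounting for 65 subjects per group in total were enrolled into this study". The next sentence turns to planned wording: "a total number of 195 subjects were to be randomly assigned".

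Two other sections give a different total. Overview of Study Design: "Total of 153 subjects who met the eligibility criteria were randomized in a ratio of 1:1:1". Method of Assigning Patients to Treatment Groups: "One hundred and fifty-three (153) subjects were enrolled in the study".

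Four further places bear on the point:
- Replacement of Subjects says that subjects who left were not replaced.
- Statistical Significance sets the primary analysis at 5%, not 2.5%.
- Changes in Conduct of the Study lists home visits, missed examinations, telephone contacts, a per-protocol sampling window and one site that was never initiated because of the lockdown. It does not mention the number of subjects.
- Change in Planned Analysis is marked as not applicable.

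**The concern.** The same verb, enrolled, is attached to 65 per group in one section and to 153 in total in another. Screen failures cannot explain the gap, because Visit 2 is titled as both the randomisation and the enrolment visit, and the 153 enrolled are the subjects who were randomised.

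Someone who reads only the sample-size section would believe that the trial had 195 subjects and a 20% cushion above the 52 evaluable per group that the 90% power rests on. With 153, the cushion is gone before the first withdrawal. The documents neither say why recruitment ended there nor state what power the design assumptions give at the number reached.

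**Working it through.** **Inputs.** From Determination of Sample Size: effect size d = 0.5, power 90%, two-sided level 2.5%, 52 evaluable per group, drop-out 20%. From Statistical Significance: level 5%. From Overview of Study Design: 153 randomised 1:1:1. Assumption: an even split of 153/3 = 51 per group, since these documents do not give group counts. With SD 1.0 at both times, d = 0.5 implies an SD of change of 1.0, that is, a before-after correlation of 0.5.

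**The plan's own figures.** The normal approximation is n = ((z₀.₉₈₇₅ + z₀.₉₀)/d)² = 49.6. For the exact figure, power(n) = P(|T| > t₁₋α/₂,ₙ₋₁), where T is noncentral t with n − 1 degrees of freedom and noncentrality d√n. This first reaches 90% at n = 53 (90.5%); n = 52 gives 89.9%. The stated 52 therefore reproduces to within one subject. Then 52/0.8 = 65, 3 × 65 = 195 and 3 × 52 = 156. The sums are correct.

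**Actual against plan.** 195 − 153 = 42 fewer randomised (153/195 = 78% of plan), and 156 − 153 = 3 fewer than the evaluable minimum. The average of 51 is below 52, so at least one group must be below 52 whatever the split. The drop-out allowance was 195 − 156 = 39 subjects, and all of it is gone.

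**Power at the number reached (d = 0.5).**

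| Evaluable per group | How it arises | Two-sided 2.5% | Two-sided 5% |
|---|---|---|---|
| 65 | planned, no loss | 95.6% | 97.8% |
| 52 | planned evaluable | 89.9% | 94.3% |
| 51 | 153 randomised, no loss | 89.2% | 93.8% |
| 44 | 7 of 51 lost | 83.6% | 90.0% |
| 43 | 8 of 51 lost | 82.6% | 89.3% |
| 41 | 20% lost (51 × 0.8 = 40.8) | 80.5% | 87.8% |
| 36 | 30% lost (51 × 0.7 = 35.7) | 74.2% | 83.1% |

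At 5%, 90% power needs 44 evaluable per group, so 51 − 44 = 7 (7/51 = 13.7%) can be lost. At 2.5% the target is missed even with no loss.

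**Does imputation restore the number?** Missing Data says: "The missing observations were imputed using Last Observation Carried Forward (LOCF) appropriately". HbA1c is scheduled only twice: "Glycated haemoglobin at Visit 1 and Visit 7". The full analysis set asks only that a subject "received at least one dose of the IP from the assigned dose by randomization, and had at least one post baseline assessment", and that assessment need not be HbA1c. A subject with no HbA1c after baseline could therefore enter with the baseline value carried forward, which is a change of zero. Suppose each of 51 subjects has a 20% chance of this and the rest have mean change 0.5 and SD 1.0:
- mean = 0.8 × 0.5 = 0.40
- variance = 0.8 × 1.0 + 0.8 × 0.2 × 0.25 = 0.84
- d = 0.40/√0.84 = 0.436

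Power is 78.7% at 2.5% and 86.4% at 5% by the noncentral t approximation, and 79.8% and 87.3% by simulation (400,000 runs). That is about the same as losing the 20% outright. Withdrawn subjects were to have the Visit 7 assessments when they left, so some would supply an early HbA1c instead; how many is not stated.

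**The case against.** - **It is protocol text put into the past tense.** The paragraph opens as an estimate, the table rows are design quantities, and 195 itself appears only with planned wording. This is probably how the phrase arose. The text still states a number as enrolled that two other sections contradict. Read wholly as a plan, it still leaves the drop from 195 to 153 unexplained.
- **The actual number is not hidden, and the rest may be reported elsewhere.** This is fair. The figure 153 is stated twice, and the text points to a separate SAP, appendices and a study report that are not part of these documents. The finding is limited to what stands here. However, the section kept for changes in conduct is here, and it is silent on the size.
- **The effect is small.** Against 52 evaluable, 51 costs less than one percentage point, and at 5% the target survives up to 7 losses per group. Both statements are true. But the plan itself expected 20% loss, and at that rate both levels fall below 90%.
- **The SD of change is assumed.** The power figures do depend on it: at 2.5% with 51 per group, a correlation of 0.25 gives 72.6% and 0.75 gives 99.6%. The effect size of 0.5 is the plan's own, however, so it is the right basis for comparing planned and actual numbers.
- **Power after the event is uninformative.** That applies to power at the observed effect. What is asked for here is the design assumption at the actual number, beside the figure already printed.

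The conflict between 2.5% and 5% and the use of LOCF are separate matters. They enter here only because the power statement depends on them.

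**Conclusion.** The point holds. It is a fault of reporting, not of arithmetic: the section presents 65 per group as enrolled when 153 in all were randomised, and its 90% power belongs to a number that was not reached. The shortfall is 42 against plan and 3 against the evaluable minimum.

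As to size, on d = 0.5 and an even split, power before losses is 89.2% at 2.5% or 93.8% at 5%. If the planned 20% is lost, it is 80.5% or 87.8%. These are scenarios and not bounds, because neither actual drop-out nor group counts are given here. The material loss is the 39-subject drop-out allowance. The planned analysis is not invalidated, but the stated size and power should be corrected.

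**What to change.** 1. In Determination of Sample Size, word 65 per group and 195 in total as planned, and label 90% as the planned power for 52 evaluable at two-sided 2.5%.
2. State that 153 were randomised, and give randomised and evaluable numbers by group or say where they are reported.
3. Reconcile the 2.5% level in that section with the 5% in Statistical Significance. At the level used for the primary analysis, state the power for the actual evaluable numbers under the same design assumptions.
4. Under Changes in Conduct of the Study, record the reduction from 195 to 153 and its reason.

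The cost is a change of wording, a short table of planned and actual numbers, and one added line. It needs no further subjects and no change to the analysis method. The downside is a smaller stated size and possibly a less favourable stated power, although at 5% with no more than 7 lost per group it would still be 90% or more.
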